3.2 STUDY DESIGN RATIONALE

We have chosen to recruit subjects age 6+ years, as there is a lower likelihood of natural resolution after this age, and safety monitoring is easier given to the ability of children of this age to communicate symptoms more clearly. Furthermore, in our experience, children of this age (and above) are more likely to understand the commitments involved in a study of this nature.

In Phase 1, children will be allocated to receive either SLIT or placebo. Placebo reactions are common in food immunotherapy, and this has not been assessed in previous CM-SLIT studies. It is therefore important to include a placebo control arm, to allow for an assessment of safety as well as efficacy. In addition, the inclusion of a placebo arm will allow us to assess for natural resolution, where a child might outgrow their CM allergy during this period, independent of any active intervention. The duration of Phase 1 will depend on each participant's initial sensitivity to CM, in order to achieve a degree of consistency in terms of duration that each participant is receiving the highest maintenance dose (target 4 months).

Data suggests that allergen exposure across the sublingual mucosa may be more likely to induce tolerance, as the sublingual region has the highest permeability within the oral mucosa, and a higher density of dendritic cells which can stimulate T-regulatory response;⁷ this might explain the efficacy of SLIT in the treatment of allergic rhinitis (hay fever). We have included a third "low dose OIT" arm in Phase 1, where the same dose of SLIT is immediately swallowed and then rinsed away (instead of being held under the tongue), as this will allow us to assess the effectiveness of the sublingual route.

Phase 2 involves all study participants undergoing 6 months of conventional OIT, thus allowing the effect of the Phase 1 treatment to be assessed. We have not included a placebo arm in Phase 2 because:

- i. Our public/patient involvement (PPI) panel felt that the inclusion of a placebo control group throughout both study phases was less acceptable and would adversely affect recruitment (since some children would undergo 3 DBPCFC but no active treatment).
- ii. There is existing data from placebo-controlled studies on the safety of conventional OIT for CM allergy; this information is not required for our primary outcome.
- iii. The protocol already allows for an assessment for natural resolution of CM allergy, given the inclusion of a control group in Phase 1.

We will use an OIT protocol in Phase 2 that has been adapted from published and unpublished data relating to eliciting doses in children with CM allergy, as well as previous OIT protocols with favourable safety data. All updosings will take place under medical supervision. We therefore expect this protocol to have a satisfactory safety profile, even for those participants randomised to the placebo group in Phase 1.

The efficacy of treatment will be assessed by double-blind, placebo-controlled food challenge (DBPCFC) at the end of each phase, an established research tool in food allergy.⁸ We have chosen a daily maintenance dose of 4000mg CM protein (roughly equivalent to 120 ml or half a cup of milk), on the basis of previous reports that this amount is generally well-tolerated by subjects undergoing OIT on a daily basis, and it is also associated with a suggestion of efficacy. Our main efficacy outcome – "successful desensitization" or ability to tolerate 8000mg CM protein – has been chosen in agreement with previous studies to allow the intake of full milk servings following the intervention. This is expected to allow dietary liberalisation, potentially leading to a positive impact on health-related quality of life.

This is a two centre study: the procedures involved are complex and require intensive clinical assessment only available at specialist allergy centres with experience in food immunotherapy. The study design allows for a more efficient use of resources and promotes consistency in clinical management. The locations (in central London and Madrid) allow for the recruitment of patients from diverse geographical areas and ethnic background.

⁷Jay DC, Nadeau KC. Curr Allergy Asthma Rep. 2014; 14:473.

⁸Plaut M, Sawyer RT, Fenton MJ. Summary of the 2008 NIAID-US FDA Workshop on Food Allergy Clinical Trial Design. J Allergy Clin Immunol 2009;124:671-8.e1.

4. STUDY POPULATION

4.1. INCLUSION CRITERIA

1. Age 6-17 years at time of consent.
2. Past history consistent with IgE-mediated allergy to CM.
3. Allergic to 1.44g CM protein (approx. 40ml fresh milk) or less, at DBPCFC prior to randomisation
4. Written, informed consent of parent/legal guardian and patient assent.

4.2. EXCLUSION CRITERIA

1. Required previous admission to an intensive care unit for management of an allergic reaction.
2. Significant symptoms of non-IgE-mediated CM allergy within the previous 12 months.
3. Children with a past history of CM allergy currently consuming CM-containing products other than extensively-heated milk in baked foods (e.g. biscuits, cakes).
4. Poorly controlled asthma within the previous 3 months (as defined by clinician judgement with reference to the ICON consensus)⁹, or asthma requiring treatment with >5 days oral corticosteroids within the previous 3 months.
5. Moderate-severe eczema, defined as requiring *more than* once daily application of 1% hydrocortisone as maintenance treatment despite appropriate use of emollients (eczema is not otherwise an exclusion criteria)
6. Clinically significant chronic illness (other than asthma, rhinitis or eczema)
7. History of symptoms of eosinophilic oesophagitis, irrespective of cause
8. Undergoing specific immunotherapy to another allergen *and* within the first year of treatment.
9. Receiving anti-IgE therapy, oral immunosuppressants, beta-blocker or ACE inhibitor.
10. Pregnancy
11. Unwilling or unable to fulfil study requirements

4.3. WITHDRAWAL CRITERIA

Subjects will be free to withdraw from the study at any time without affecting their future medical care. Subjects who are withdrawn from active treatment will be invited to remain in the study for assessment of outcome relating to safety and HRQL measures (HRQL will be assessed 3 months after withdrawal).

The safety of study participants is paramount in this study: subjects who are assessed as having had anaphylaxis to a home dose but who do not receive IM adrenaline as per the management plan will have further updosing suspended until the family undergo retraining on the recognition and management of allergic symptoms.

A participant will be withdrawn from the study under the following circumstances:

- If, in the opinion of the study team, compliance with study procedures is suboptimal such that it compromises the patient's safety.
- If, in the opinion of the study team, further participation would adversely affect the participant's health.
- A child develops an exclusion criteria during the updosing phase of the study e.g. a new medication (which would normally be a contra-indication) is commenced.
- If consent is withdrawn or the subject fails to return for a study visit without due reason.

Any subject excluded from further participation will not be replaced, unless withdrawal occurs after initial DBPCFC but prior to allocation to treatment.

⁹Papadopoulos NG, Arakawa H, Carlsen KH, et al. International consensus on (ICON) pediatric asthma. *Allergy*. 2012;67:976-97.

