6. ADVERSE EVENT REPORTING

6.1 DEFINITIONS

An **adverse event** (AE) is any occurrence or worsening of an undesirable or unintended sign symptom, laboratory finding or disease that occurs during participation including occurrences that are not necessarily caused by or related to a study intervention. An adverse event will be followed until it resolves or until 30 days after a participant terminates from the study whichever comes first.

A **serious adverse event** (SAE) is defined as any adverse event that suggests a significant hazard. This includes but is not limited to any of the following:

1. Death: Any death that occurs during the study must be reported whether considered treatment related or not.
2. A life-threatening event: Any adverse therapy experience that in the view of the investigator places the participant at immediate risk of death from the reaction as it occurred. In line with guidance from the Food and Drug Administration (FDA) for Industry and Investigators²⁵, “it does not include an adverse event or suspected adverse reaction that, had it occurred in a more severe form, might have caused death.”
3. Inpatient hospitalization or prolongation of existing hospitalization.
4. Persistent or significant disability.
5. An event that requires intervention to prevent permanent impairment or damage. An important medical event that may not result in death, be life threatening or require hospitalization may be considered an SAE when based on appropriate medical judgment, it may jeopardize the participant and may require medical or surgical intervention to prevent one of the outcomes listed above.
6. Important AEs that are not immediately life-threatening or do not result in death or hospitalization but may jeopardise the subject or may require intervention to prevent one of the other outcomes listed in the definition above should also be considered serious.

The adverse event can be described as ‘**expected**’ if it caused symptoms and/or signs that could be reasonably described as a consequence of an allergic reaction to allergen exposure within the protocol. Symptoms of an allergic reaction are defined as any described within this protocol.

An adverse event is considered “**unexpected**” when its nature or severity is not consistent with the investigator’s protocol.

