An adverse event is defined as “**related**” when it has resulted from the administration of any of the research procedures. Related adverse events are defined as “**adverse reactions**”.

²⁵ 2012 Food and Drug Administration (FDA) Guidance for Industry and Investigators, “Safety Reporting Requirements for INDs and bioavailability studies

All episodes of anaphylaxis occurring in response to a dose of SLIT/OIT will be treated as an AE "of interest" and reviewed by the Trial Management team.

The following criteria will constitute an SAE:

- Anaphylaxis occurring at in-hospital challenge *requiring* three or more doses of intramuscular adrenaline
- Anaphylaxis occurring in response to a dose of SLIT/OIT outside the hospital environment, requiring more than one dose of intramuscular adrenaline. **Such reactions will be classified as a SERIOUS ADVERSE REACTION.**
- Clinician-confirmed diagnosis of eosinophilic oesophagitis (with positive histology).

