7.2 STATISTICAL ANALYSIS PLAN

Data will be collected on electronic clinical records or paper CRFs which include the patients name, DOB and hospital number. Participants will be assigned a study number which will be noted on all records. Data will then be entered on to a password-protected computer database on the secure hospital IT system; only the study number will be used to identify the patient data.

De-identified data and all appropriate documentation will be stored for a minimum of 10 years after the completion of the study including the follow-up period.

The primary analysis will be performed on an intention-to-treat basis, irrespective of compliance and whether or not they have completed the prescribed regimen. A secondary analysis will also be performed on a per-protocol basis.

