8.8 PROTOCOL COMPLIANCE

Every effort will be made to adhere to the study protocol and participants who are non-compliant with the protocol will be withdrawn after review and agreement between the 2 principle investigators. Protocol deviations may be captured from a variety of different sources including CRFs, EPR, communications and updates. The sponsor will maintain a log of the non-compliances to ascertain if there are any trends which need to be escalated. The sponsor will assess the non-compliances and action a timeframe in which they need to be dealt with. Each action will be given a different timeframe dependent on the severity. If the actions are not dealt with accordingly, the Research Compliance Office will agree an appropriate action, including an on-site audit.

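### Section 4.3 takes children out of the study, not only off treatment, for conditions that milk dosing could provoke, and adverse-event follow-up has no single end point

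*Combined protocol and SAP*

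**What the plan says.** Section 4.3 opens with a retention provision: "Subjects who are withdrawn from active treatment will be invited to remain in the study for assessment of outcome relating to safety and HRQL measures", with quality of life (HRQL) assessed three months after withdrawal. It then states: "A participant will be withdrawn from the study under the following circumstances". The circumstances listed are:

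- compliance poor enough to compromise safety;
- the team's view that continuing would harm the child's health;
- "A child develops an exclusion criteria during the updosing phase of the study", with a newly started contraindicated medicine as the example;
- withdrawn consent, or an unexplained failure to return.

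Section 8.8 adds that "participants who are non-compliant with the protocol will be withdrawn after review and agreement between the 2 principle investigators". It does not say whether that means from treatment or from the study.

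Among the exclusion criteria in 4.2, number 7 is "History of symptoms of eosinophilic oesophagitis, irrespective of cause". Numbers 2, 4 and 5 cover significant non-IgE symptoms, poorly controlled asthma and moderate-severe eczema. The definitions in section 6.1 make eosinophilic oesophagitis a serious adverse event (SAE) once a clinician has diagnosed it and histology is positive.

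On follow-up, 6.1 says: "An adverse event will be followed until it resolves or until 30 days after a participant terminates from the study whichever comes first". Section 6.2 instead counts 30 days from completion of study treatment. Table 1 lists adverse events (AEs) at the final contact at about 15 months.

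Section 7.2 commits the primary analysis to intention to treat (ITT), "irrespective of compliance and whether or not they have completed the prescribed regimen". The primary outcome (3.1.1) is measured in Phase 2 only and compares group S with group C.

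**The concern.** The listed triggers say the child leaves the study; the opening sentence of the same section speaks of leaving treatment. A site applying the list as written would stop observing a child because that child developed a condition which may be a harm of the intervention. The protocol treats eosinophilic oesophagitis as a harm to watch for, since it names it as an SAE. For the other three conditions the link to dosing is my inference, although 5.3.3 already describes wheeze, skin and abdominal symptoms as reactions to doses.

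Two things are at stake. First, the safety record may be cut short for the children whose later course matters most. Second, in Phase 1 groups S and O receive milk and group C receives placebo. Removals provoked by milk before Phase 2 could therefore thin out group S and not group C, leaving the primary comparison with missing outcomes related to treatment.

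**Working it through.** **1. Which text governs a withdrawn child?**

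| Section | Who is covered | What follows |
|---|---|---|
| 4.3, opening | withdrawn from active treatment | invited to stay for safety and HRQL; only HRQL has a time point (3 months) |
| 4.3, list | the four circumstances | out of the study |
| 5.8.2 | out of the study after a significant allergic reaction | contact at 3 months, HRQL only |
| 8.2 | clinician gives alternative treatment | stays for follow-up and analysis |
| 8.8 | non-compliant | withdrawn if both investigators agree; from what is not stated |

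No row gives a safety follow-up schedule to a child who meets an exclusion criterion during updosing.

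**2. When does AE collection end?**

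- Child who completes, treatment taken as ending at the exit challenge (about month 12): under 6.2, 12 months + 30 days, about month 13; under Table 1, about month 15; under 6.1, 15 months + 30 days, about month 16.
- Child removed at the end of Phase 1 updosing (week 12, from 5.3.2.1): 12 × 7 + 30 = day 114, about 3.7 months. Phase 1 is planned to last (12 + 16) × 7 = 196 days, so collection stops 196 − 114 = 82 days before Phase 1 would have ended. Against 15 months, 15 − 3.7 = about 11 months are unobserved, including the whole primary-endpoint window.
- Child removed two months into Phase 2 (start at about month 6 in Table 1): 6 + 2 = month 8, plus 30 days = month 9. This leaves 15 − 9 = about 6 months unobserved.

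**3. Eosinophilic oesophagitis.** Exclusion 7 needs symptoms only; the SAE needs histology. The symptoms would be recorded as an AE under 6.2, and histology within 30 days would be captured. Histology later than that, in a child who has left the study, has no stated route to the record.

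**4. What missing Phase 2 outcomes could do.** The plan's figure is 66, so 66 / 3 = 22 per arm. Section 7.1 gives 70% versus 18%, alpha 0.01666, 80% power and 10% loss, without stating sidedness. The usual two-proportion formula with continuity correction gives 19 per arm one-sided, and 19 / 0.9 rounds up to 22. Two-sided, it gives 22 before any allowance for loss. The 66 is therefore reproduced only under one of these variants. It is not disputed here.

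One child is 1 / 22 = 4.5 percentage points of an arm. The loss allowance is 0.10 × 22 = 2.2 children. Expected events in S are 0.18 × 22 = 3.96, about 4. Suppose (assumption) two S children are removed in Phase 1 and none in C. The observed S rate is then:

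| The two removed children | Left out | Counted as no event | Counted as event |
|---|---|---|---|
| would both have had an event | 2/20 = 10.0% | 2/22 = 9.1% | 4/22 = 18.2% |
| would both have had none | 4/20 = 20.0% | 4/22 = 18.2% | 6/22 = 27.3% |

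The plan gives no rule for choosing a column.

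Power was computed exactly for the two-sided Fisher test by summing Bin(x; n, p_C) × Bin(y; n, p_S) over all tables with p below alpha. Loss is assumed equal in both arms. Results are shown at alpha 0.01666 / 0.05, because 7.1 and 7.2.1 use different levels.

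| Loss (assumed) | Left out | All 22 kept, counted as no event | All 22 kept, counted as event |
|---|---|---|---|
| none | 85% / 92% | same | same |
| 10% | 77% / 88% (20 per arm) | 75% / 85% (63% v 16.2%) | 74% / 83% (73% v 26.2%) |
| 20% | 70% / 87% (18 per arm) | 63% / 77% (56% v 14.4%) | 60% / 72% (76% v 34.4%) |

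The rates in brackets are 0.70 and 0.18 multiplied by (1 − loss), plus the loss itself where removal counts as an event.

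**The case against.** The best defence is that the protocol, read as a whole, means to stop treatment and keep following. Section 4.3 opens that way. Section 8.2 keeps children in follow-up when the clinician departs from protocol treatment. Section 5.8.2 plans contact with some children described as out of the study, so that phrase does not always mean contact ends. A sensible site could work on that reading. It remains one reading: the three provisions cover different groups, and none gives AE follow-up to the children in the 4.3 list.

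Several limits on the concern stand:

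- The exclusion-criterion trigger covers updosing only, and its one example is a new medicine.
- Removal under 8.8 needs agreement between two investigators.
- A harm in Phase 2 is recorded before the child leaves. If it is graded above transient, the child already counts as a primary event. The primary endpoint is therefore exposed mainly through removals before Phase 2.
- Group C children may also meet an exclusion criterion, so an imbalance is possible but not shown.

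A reader might infer that the ITT commitment is breached. The documents do not support that: nothing removes a withdrawn child from the analysis set, and not replacing withdrawn children is compatible with ITT. A reader might also infer that the oesophagitis SAE would be lost. That needs histology later than 30 days in a child who is no longer followed, and the documents give no time from symptoms to biopsy. Nor can the missed-visit trigger be sized: no visit count or missed-visit rate is stated, and unexplained failure to return may mean lost contact, not one missed appointment.

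**Conclusion.** The concern holds as a conflict in the text with a real consequence for safety data. Section 4.3 does not separate stopping treatment from leaving the study, and 6.1, 6.2 and Table 1 give three different ends to AE collection. Applied literally, the rule leaves about 11 months unobserved for a child removed at week 12 of Phase 1 and about 6 months for one removed two months into Phase 2. Withdrawn children remain in the ITT set, but some of their outcomes may be missing, so the ITT analysis may not be fully deliverable.

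The number of children affected is unknown. The S-rate range of 9.1% to 27.3% and the power figures rest on assumed removals and show sensitivity; they do not predict what will happen. That milk dosing can provoke the listed conditions, and that removals would differ between S and C, are plausible but not established by the documents. The point is worth acting on because the primary outcome is safety and the remedy is cheap.

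**What to change.** In 4.3 and 8.8, state that every listed trigger except withdrawal of consent ends study treatment only, and that the child stays in the study for AE and HRQL follow-up to the 15-month contact already scheduled. Reconcile 6.1, 6.2 and Table 1 to one end point for AE follow-up, with AEs unresolved at withdrawal followed to resolution, diagnosis or the 15-month contact. Align 5.8.2 and 8.2 with that wording. Decisions on stopping dosing and on doing the exit challenge stay with the investigators under the existing text.

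The cost is an edit to these sections and a few extra telephone or email contacts; 5.7 already allows the 15-month HRQL assessment by email or online. The change has a limit: follow-up cannot create a Phase 2 dosing outcome for a child who never starts Phase 2. How such a child is counted is a separate rule that the analysis plan still has to state.

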5 STUDY PROCEDURES

The study visits and procedures are summarised in Table 1 and Figure 2.

Approx month	0m		Day 1		~6m			~12m	~15m
	Screening	Baseline DBPCFC	Escalation visit	Updosing visits	Interim DBPCFC	Escalation visit	Updosing visits	Exit DBPCFC	Final HRQL assessment
General									
Informed consent/assent	X								
Medical history	X								
Allergy / diet history	X								
Directed physical exam	X	X	X	X	X	X	X	X	
Vital signs	X	X	X	X	X	X	X	X	
Asthma control questionnaire	X	(X)			(X)			(X)	
SCORAD	X								
Spirometry	X	(X)			(X)			(X)	
Peak Flow	X	X	X	X	X	X	X	X	
Adverse events			X	X	X	X	X	X	X
Concomitant medications	X	X	X	X	X	X	X	X	X
Skin prick tests (SPT)	X	X [#]			X			X	
Blood test / cannulation	(X)*	(X)*			X			X	
Full blood count	(X)*	(X)*							
Urine pregnancy test	(X)								
Saliva collection	X				X			X	
Stool collection		X*							
Intervention									
Allocation				X					
SLIT/OIT			X	X		X	X		
Outcomes									
DBPCFC (2 visits)		X			X			X	
HRQL assessments	X		X		X			X	X
SPT panel (including titrated SPT)	X				X			X	
SPT to fresh CM	X	X							
Serum IgE/IgG4	X*	X*			X			X	
Other laboratory test		X [§]			X [§]			X [§]	

Table 1: Study procedures

*may be tested at either visit, depending on local centre and patient preference

[#] limited skin prick testing only during each challenge at baseline

(X) will be performed depending on clinical need / local SOP

[§]London centre only

[figure not shown]

Figure 2: Study flowchart and interventions

